10.1.2. Treatment Modifications

Treatment modifications included any dose delays, reductions, and interruptions will be summarized. The following parameters will be summarized by study drug, as applicable.

10.1.3. Dose Delays

Number of dose delays per patient, length of delay, and reason for delay will be summarized for each drug component for each treatment arm.

10.1.4. Dose Interruptions

Only drug components in FOLFOX can be interrupted. Number of patients with at least 1 dose interruption, reason for interruption, and number of interruptions per patient will be summarized for FOLFOX arm.

10.1.4.1. Dose Reductions

Each drug component may be reduced. Number of patients with at least 1 dose reduction, reason for reductions, and number of dose reductions will be summarized for each treatment arm for

each component of treatment. Each FOLFOX dose reduction level is defined in protocol Table 12.

11. Efficacy Analysis

All efficacy analyses will be based on the ITT population.

11.1. Primary Efficacy Analysis

The primary endpoint is OS. Overall survival is defined as the time from date of randomization to the date of death (due to any cause). For patients whose last known status is alive at the data cutoff date for the analysis, time will be censored as the last contact date prior to the data cutoff date.

The null (H_o) and alternative (H_a) hypotheses for testing overall survival are:

H_o: HR pegilodecakin + FOLFOX/FOLFOX alone = 1 H_a: HR pegilodecakin + FOLFOX/FOLFOX alone \neq 1 (superiority)

The hypotheses will be tested using a 2-sided stratified log-rank test. The stratification factors from IVRS will be used. Kaplan-Meier (K-M)estimates for the median time along with 95% CIs for each randomized arm; the hazard ratio with 95% CI will be provided as well.

Survival rates at fixed time points (3 months, 9 months, 12 months, 15 months, etc.) will be estimated using K-M estimate for each treatment group. These rates will be compared based on a normal approximation for the difference between the treatment arms. Associated 2-sided 95% CI will be calculated.

Hazard ratios for overall survival and their 95% CIs will be provided using Cox proportionalhazard model(Cox 1972) with treatment, stratification factors (from IVRS).

11.1.1. Subgroup Analyses

Subgroup analysis for the primary endpoint (OS) will be performed and the HR and 95% CI will also be provided for each treatment arm in the forest plot. Subgroups are defined as follows:

- prior therapy
 - o prior single agent gemcitabine therapy versus
 - o Gemcitabine/nab-paclitaxel therapy
- geographic region
 - North America
 - o Europe
 - Asia-Pacific
- age group at baseline
 - o <65 years
 - $\circ \geq 65$ years

- sex
 - o female
 - o male
- race (White, Asian, other)
 - o White
 - o Asian
 - o other
- baseline level of CA19-9
 - \circ normal
 - \circ >normal \leq (59 * Upper limit Normal [ULN])
 - o >59 * ULN
- Number of metastatic sites
 - \circ 1 site
 - o 2 sites
 - $\circ \geq 3$ sites
- Location of primary lesions in pancreas
 - o head
 - o other
- liver metastases
 - o yes
 - o no
- time from initial diagnosis (<6 months, \geq 6 months)
 - \circ <6 months
 - $\circ \geq 6$ months
- Eastern Cooperative Oncology Group
 - o 0
 - o 1
- weight
 - $\circ \leq 80 \text{kg}$
 - >80 kg

If a subgroup category has less than 10 patients per treatment arm, HR will not be computed/displayed. A forest plot will be provided based on the HRs for the subgroup analyses.

11.2. Secondary Efficacy Endpoints

The secondary efficacy endpoints are PFS and ORR, DCR, DoR and 1-year OS rate.

11.2.1. Progression-Free Survival

Progression-free survival is defined as the time from randomization to the date of the first documented tumor progression as determined by the investigator (per RECIST v1.1 criteria) or death due to any cause - whichever occurs first.

The recorded date of radiographic progression is the date of the tumor assessment visit at which progression is declared. Only adequate tumor assessments (ATAs) will be considered in the determination of radiographic progression and censoring date. Adequate tumor assessments is defined as assessment at a time point evaluation of CR, PR, SD (non-CR, non-PD), or progression.

The censoring rules are:

- Patients who do not progress or die as of the data cutoff date will be censored on the date of their last ATA on or prior to the data cutoff date.
- Patients who do not have any baseline tumor assessment will be censored on the date they are randomized with a duration of 1 day.
- Patients who do not have any on-study tumor assessment and do not die will be censored on the date they are randomized with a duration of 1 day.
- Patients who received any subsequent anti-cancer therapy will be censored on the date of last ATA on or prior to initiation of the subsequent anti-cancer therapy.
- Patients who are lost to follow for more than 1 scheduled visit (greater than (7*8*2+2*3)=118 days from the previous ATA date) prior to progression disease or death will be censored on the date of last ATA prior to the missing scheduled visits.

In the event of suspected pseudoprogression

- If a consecutive sequence of pseudoprogression is confirmed with a confirmatory scan, the date of progression used to determine PFS will be the date of the first consecutive pseudoprogression, not the date of the confirmatory scan.
- If no additional scan is available after the initial suspected pseudoprogression, the initial PD data will be considered as PD date.
- If the pseudoprogression is not confirmed for the following scan, the patient will continue to be followed up for future scans. Multiple pseudoprogression's can occur for a patient during the study until disease progression is confirmed or the patient lost to follow up.

The K-M estimates for the median, the first and third quartiles with 95% CI (if estimable), along with the HR (including 95% CI), will be provided. The figure of K-M curve will also be

presented for each randomized arm and the difference in the curves will be tested using the stratified log-rank test, with the same strata as in OS. In addition forest plot will be provided for the PFS based on the HRs for the subgroup analyses.

11.2.2. Objective Response Rate

Objective response rate is defined as the proportion of patients with a confirmed CR or confirmed PR relative to the total analysis population. Responses observed at each time point while on study treatment (but before the time of disease progression[defined in 10.2.1] or the initiation of post discontinuation therapy) will be included in the derivation.

Objective response rate will be summarized along with the exact 95% CI by randomized arm. A stratified Cochran-Mantel-Haenszel (CMH) test will be used to compare ORR between 2 randomized arms by the same stratification factors as OS. The odds ratio with 95% CI will be provided.

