6.2 Study Drug Treatments

The following procedures will be conducted after patient eligibility has been established.

Patients will be randomized within 21 days of obtaining their screening assessments. All patients must begin study treatments within 3 days after the date of Randomization. Please see the Pharmacy Manual for details.

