7.4.1.2.2 Objective Response Rate

Objective response rate is defined as the proportion of patients with a confirmed CR or confirmed PR relative to the total analysis population. Best overall response is defined as the best response as determined by the Investigator, recorded between the date of Randomization and the date of objectively documented progression per RECIST v.1.1 or the date of subsequent therapy, whichever occurs first. For patients without documented progression or subsequent anti-cancer therapy, all available response assessments will contribute to the BOR determination. Complete or partial responses may be claimed only if the criteria for each are met at a subsequent time point as specified in the protocol (approximately 4 weeks later). For patients who continue AM0010 in combination with FOLFOX treatment beyond progression due to suspected “pseudoprogression,” the BOR should be determined based on response assessment recorded at the next scheduled CT scan, which is done approximately 4 weeks after pseudoprogression to assess BOR. If the patient subsequently responds or returns to baseline, that assessment of objective tumor response is achieved after pseudoprogression as the response. Designation of best response of SD requires the criteria to be met at least 8 weeks (± 3 days) after Randomization.

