6.4. Treatment Duration

Each cycle is 14 days, with Days 6, 7, 13, and 14 being rest days for pegilodecakin. FOLFOX will be administered on Day 1 of each cycle. Patients randomized to the investigational combination treatment (pegilodecakin plus FOLFOX) ARM 1, after completion of up to 12 cycles of combination chemotherapy or if experiencing chemotherapy intolerance (as defined as Grade 3 or 4 non-hematologic toxicity that has not resolved to baseline in 28 days or Grade 4 hematologic toxicity that has not resolved to baseline in 28 days) may continue to receive maintenance pegilodecakin if the patient continues to receive clinical benefit (CR, PR, or stable disease [SD]). Patients will be treated until tumor progression by RECIST v.1.1. For ARM 2 (FOLFOX only) patients may receive FOLFOX for up to 12 cycles or 24 weeks or until tumor progression by RECISIT v.1.1 or until patients experience unacceptable toxicity, require palliative radiotherapy, withdraw consent, or their physician feels it is no longer in their best interest to continue on study treatments whichever occurs earlier.

To mitigate the chance of detecting false-progression (ie, pseudoprogression) early in the course of treatment on ARM 1 with pegilodecakin in combination with FOLFOX, patients whose scans show radiographic progression in the absence of clinical deterioration including worsening Eastern Cooperative Oncology Group (ECOG) Performance Status (PS) as assessed by the Investigator may remain on study treatments and should have an additional scan 4 weeks (±3 days) later as outlined in protocol Section 8.1.1. If this subsequent scan shows disease progression, the patient will be discontinued from study treatments.

7. General Statistical Considerations

7.1. Population:

The enrolled population includes all patients who sign the informed consent document.

The intent-to-treat (ITT) population includes all randomized patients per interactive voice response system (IVRS).

The safety population includes all randomized patients who received any amount of pegilodecakin or FOLFOX.

Per-Protocol Population: All patients who are in the safety population and have no major protocol deviations.

The major protocol deviations which will result in exclusion from the Per-Protocol population are listed below. This is not an exhausted list and may be amended over the course of the trial.

- patients with disease other than metastatic pancreatic adenocarcinoma
- patients with ECOG >1 at baseline

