11.3.2. Duration of Response, Time to Response

Analyses of duration of response and time to response will only include patients with confirmed CR or PR based on investigator's assessments.

The duration of response is defined as the time from the date of the first documentation of objective tumor response (CR or PR) as determined by the investigator using RECIST v1.1, that is subsequently confirmed to the date of the first documentation of objective tumor progression or to death due to any cause, whichever occurs first.

Duration of response will be censored on the date of the last adequate tumor assessment on study for patients who do not have tumor progression and who do not die due to any cause while on study. Duration of response will be censored according to the same rules as PFS.

Duration of response will be summarized descriptively using the K-M method for each randomized arm, including the median, the first and third quartiles along with 95% CI (if estimable).

Time to response is defined as the time from date of randomization to the date of the first documentation of objective tumor response that is subsequently confirmed. Descriptive statistics will be summarized for time to response.

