11.3.3. Best Overall Response

Best overall response (BOR) is defined as the best response as determined by the investigator, recorded between the date of randomization and the date of objectively documented progression per RECIST v1.1 or the date of subsequent therapy, whichever occurs first. For patients without documented progression or subsequent anti-cancer therapy, all available response assessments will contribute to the BOR determination. Complete or PRs may be claimed only if the criteria for each are met at a subsequent time point as specified in the protocol (approximately 4 weeks later).

For patients who continue pegilodecakin in combination with FOLFOX treatment beyond suspected pseudoprogression, if the pseudoprogression is not confirmed in the following scan, the additional responses occurred after the pseudoprogression should be considered in deriving BOR.

Confirmed responses are those that persist on repeat imaging study 4 weeks after initial documentation of response. Designation of best response of SD requires the criteria to be met at least 8 weeks (\pm 3 days) after randomization. Designation of best response of SD requires the criteria to be met at least 8 weeks (\pm 3 days) after randomization.

Best overall response will be summarized along with the exact 95% CI by randomized arm.

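### SAP 11.2.2 counts responses for ORR only while on study treatment, contradicting protocol 7.4.1.2.2 and SAP 11.3.3; read literally, Arm 1 has the longer maximum window

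*SAP*

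**What the plan says.** The SAP's ORR section (11.2.2) defines ORR as the proportion with confirmed CR or PR and then states which assessments enter: "Responses observed at each time point while on study treatment (but before the time of disease progression", as defined in a cited section 10.2.1, or before therapy given after discontinuation.

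The SAP's section on best overall response (BOR, 11.3.3) uses another window: the best response "recorded between the date of randomization and the date of objectively documented progression per RECIST v1.1 or the date of subsequent therapy, whichever occurs first". Protocol 7.4.1.2.2, which is the protocol's own ORR section, has the same window and adds: "For patients without documented progression or subsequent anti-cancer therapy, all available response assessments will contribute to the BOR determination". Neither mentions treatment status.

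BOR has its own table: "Best overall response will be summarized along with the exact 95% CI by randomized arm". For duration of response (DoR) and time to response, SAP 11.3.2 says: "Analyses of duration of response and time to response will only include patients with confirmed CR or PR". It does not say under which window those responses are identified.

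On treatment length, SAP 6.4 says that Arm 1 patients, after FOLFOX ends, "may continue to receive maintenance pegilodecakin if the patient continues to receive clinical benefit". For the control arm: "For ARM 2 (FOLFOX only) patients may receive FOLFOX for up to 12 cycles or 24 weeks". Protocol 6.6.1 treats a patient who continues any component as still on the study regimen. It also requires 8-weekly scans after treatment stops without progression, until progression or a new anti-cancer therapy.

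**The concern.** Two definitions of the same responses sit in one SAP. ORR is the last endpoint in the type-I-error-controlled hierarchy of SAP 11.4, so its numerator should be fixed without ambiguity before unblinding.

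Three things are at stake:

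- **Internal consistency.** The ORR numerator can differ from the CR+PR count in the BOR table, and it is open which set of responders enters DoR and time to response. The disease control rate is analysed in the same manner as ORR (SAP 11.3.1), so it may inherit the restriction.
- **Comparability of the arms.** Taken literally, the window is tied to time on treatment, and only Arm 1 has a treatment phase after FOLFOX. In an open-label trial, the window would then depend on treatment decisions made after randomization.
- **Confirmation.** SAP 11.2.2 does not say whether the confirmatory scan must also fall on treatment.

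**Working it through.** **1. The plan's own figure.** Control treatment lasts at most 12 cycles × 14 days = 168 days; 168 / 7 = 24 weeks. This matches SAP 6.4.

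**2. Is there a scan that separates the arms?** Days are counted from randomization. Protocol 6.2 says: "All patients must begin study treatments within 3 days after the date of Randomization". Treatment therefore starts on day 0–3.

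- The 12-cycle period ends, without dose delays, by day 168 + 3 = 171 at the latest.
- The week-32 scan is due on day 32 × 7 = 224, ±3 days, so day 221 at the earliest.
- The gap is at least 221 − 171 = 50 days.
- Protocol 6.2.2.2 allows ±3 days per cycle. If all 11 intervals between cycles used the full +3 days, the period would end 33 days later, and the gap would still be at least 50 − 33 = 17 days.

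A first response at week 32 is therefore off treatment for such an Arm 2 patient and on treatment for an Arm 1 patient on maintenance. If confirmation must also be on treatment, an on-schedule Arm 2 response first seen at week 24 fails too, because it can be confirmed only about 4 weeks later, near week 28. Only responses first seen at week 8 or 16 would then be safe.

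**3. How large could the effect be?** The documents give no assumed ORR and no response timing for this trial, so the loss rates below are assumptions. The calculation uses 283 patients per arm and equal true ORR *r* of 2%, 3% or 5%. Counted responders are binomial with probability *r* × (1 − loss). The test is the unstratified pooled z-test at ±1.96, a stand-in for the stratified CMH test, with error rates summed exactly over both binomial distributions.

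| Assumed loss of responders | ORR | Error favouring Arm 1 | Error favouring control | Total |
|---|---|---|---|---|
| None | 2% | 0.0242 | 0.0242 | 0.0484 |
| | 3% | 0.0254 | 0.0254 | 0.0507 |
| | 5% | 0.0248 | 0.0248 | 0.0496 |
| Control 10%, Arm 1 0% | 2% | 0.0351 | 0.0158 | 0.0509 |
| | 3% | 0.0407 | 0.0153 | 0.0561 |
| | 5% | 0.0456 | 0.0125 | 0.0581 |
| Control 5%, Arm 1 0% | 2% | 0.0292 | 0.0197 | 0.0488 |
| | 3% | 0.0322 | 0.0199 | 0.0521 |
| | 5% | 0.0338 | 0.0178 | 0.0516 |
| Control 5%, Arm 1 10% | 2% | 0.0192 | 0.0288 | 0.0481 |
| | 3% | 0.0198 | 0.0325 | 0.0523 |
| | 5% | 0.0176 | 0.0339 | 0.0515 |

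A 10% loss in control means 283 × 0.02 × 0.10 = 0.57 patients at 2%, 0.85 at 3% and 1.42 at 5%. The last block reverses the direction. It is included because protocol 5.3 lets toxicity delays end treatment early in Arm 1 as well.

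**4. Is a low ORR range plausible?** The second-line FOLFOX series in protocol 1.1.1 reports no objective responses among 27 treated patients. Its disease control rate of 36% fits 9/25 but no count out of 27 (9/27 = 33.3%, 10/27 = 37.0%), so the evaluable denominator is unclear. The exact 95% upper limit for zero responses is 1 − 0.025^(1/27) = 12.8%, or 1 − 0.025^(1/25) = 13.7%. The 2–5% range lies within these limits but remains an assumption.

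**The case against.** The best counter-argument is that the literal reading fits its own sentence badly. SAP 11.2.2 also ends the window at therapy given after discontinuation, which would be nearly redundant if responses stopped counting when treatment stopped. Protocol 7.4.1.2.2 and SAP 11.3.3 agree with each other, and off-treatment scans are required, so the intended rule can be guessed. That stands as evidence of loose wording. It does not settle the matter: protocol 7.5.4 leaves the details of ORR testing to the SAP, and 11.2.2 is the SAP's ORR derivation.

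It is also fair that neither document defines the end of study treatment. That Arm 2 is off treatment once all FOLFOX components stop is an inference from protocol 6.6.1. The undefined term is a further reason not to hang the endpoint on it.

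The week-32 case is narrow: it needs a control patient who completes 12 cycles on schedule, without progression or new therapy, and then responds for the first time. With median PFS of 1.7–3.0 months in the cited FOLFOX series, few patients would get there. The end-of-treatment scan (protocol 6.5) would also catch many responses present at stopping. The loss rates are assumed, and the error rates ignore that ORR is tested only after significant OS and PFS. All of this limits the size of the problem and leaves the contradiction in place.

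Finally, one common rule does not give equal follow-up, since the window still closes at new therapy, which Arm 2 completers may start while Arm 1 continues maintenance. That is correct. The fix removes the conflict and the treatment-based cap, not every difference in follow-up.

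**Conclusion.** The concern holds. SAP 11.2.2 contradicts both protocol 7.4.1.2.2 and SAP 11.3.3, and this does not depend on the size or direction of any bias. On a literal reading, the maximum response window is longer in Arm 1; that part rests on treating Arm 2 as off treatment after its last FOLFOX cycle.

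The longer maximum would be expected to favour Arm 1, but the net direction cannot be derived, because maintenance is optional and early stopping can occur in either arm. The effect on the ORR test is probably small: under the assumed losses, total two-sided error stays between 4.8% and 5.8%, against 4.8–5.1% with no loss. The primary endpoint is not touched. The plan should be corrected because the endpoint is formally tested and the tables may otherwise disagree.

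**What to change.** In SAP 11.2.2:

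- Delete the four words *while on study treatment*.
- Apply the window of protocol 7.4.1.2.2 and SAP 11.3.3 (randomization to documented progression or start of subsequent anti-cancer therapy) to the first and the confirmatory scan, in both arms, regardless of treatment status.
- State that the ORR numerator is the number of patients whose BOR under 11.3.3 is confirmed CR or PR, and that DoR and time to response use the same patients.
- Correct the cross-reference for progression from 10.2.1 to 11.2.1, where PFS is defined.

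The cost is SAP wording only. The 8-weekly scans after treatment stops are already required in both arms, so no new data are needed.

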11.3. Other Efficacy Analysis

11.3.1. Disease Control Rate

Disease control rate, defined as the proportion of patients who achieve confirmed CR, or confirmed PR, or SD assessed by investigator according to RECIST 1.1. Disease control rate will be analyzed in the same manner as ORR.

11.3.2. Duration of Response, Time to Response

Analyses of duration of response and time to response will only include patients with confirmed CR or PR based on investigator's assessments.

The duration of response is defined as the time from the date of the first documentation of objective tumor response (CR or PR) as determined by the investigator using RECIST v1.1, that is subsequently confirmed to the date of the first documentation of objective tumor progression or to death due to any cause, whichever occurs first.

Duration of response will be censored on the date of the last adequate tumor assessment on study for patients who do not have tumor progression and who do not die due to any cause while on study. Duration of response will be censored according to the same rules as PFS.

Duration of response will be summarized descriptively using the K-M method for each randomized arm, including the median, the first and third quartiles along with 95% CI (if estimable).

Time to response is defined as the time from date of randomization to the date of the first documentation of objective tumor response that is subsequently confirmed. Descriptive statistics will be summarized for time to response.

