7.4.1.2.4 Duration of Response

Duration of response is defined as the time from the date of the first documentation of objective tumor response (CR or PR), as determined by the Investigator using RECIST v.1.1, that is

subsequently confirmed to the date of the first documentation of objective tumor progression or to death due to any cause, whichever occurs first.

7.4.1.2.5 1-Year Overall Survival Rate

The 1-year OS rate is estimated using the Kaplan-Meier method.

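### Duration of response ends at the first documented progression, while PFS and best response disregard a progression that the next scan does not confirm; the SAP never ties the DoR end date to the PFS date.

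*SAP*

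**What the plan says.** **DoR.** SAP 11.3.2 restricts the analysis to confirmed responders: "Analyses of duration of response and time to response will only include patients with confirmed CR or PR". The clock starts at the first documented CR or PR and stops at "the date of the first documentation of objective tumor progression or to death due to any cause, whichever occurs first". Protocol 7.4.1.2.4 has the same stopping rule for a response that is "subsequently confirmed to the date of the first documentation of objective tumor progression or to death due to any cause, whichever occurs first", and protocol 2.3.2, protocol 7.5.4.5 and SAP 6.2.2 agree. None of these sections mentions confirmation of progression or pseudoprogression. The only link to PFS is "Duration of response will be censored according to the same rules as PFS".

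**PFS.** SAP 11.2.1 opens in much the same terms, with "the date of the first documented tumor progression as determined by the investigator". A separate set of bullets on suspected pseudoprogression, placed after the censoring list, then modifies this. A confirmed PD is dated at its first appearance. With no later scan, "If no additional scan is available after the initial suspected pseudoprogression, the initial PD data will be considered as PD date". Otherwise, "If the pseudoprogression is not confirmed for the following scan, the patient will continue to be followed up for future scans". Protocol 2.3.2 makes the same distinction within one list of endpoints: PFS needs a definitive, confirmed progression, and DoR carries no such qualifier.

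**Best response.** Under SAP 11.3.3, when the next scan does not confirm the PD, "the additional responses occurred after the pseudoprogression should be considered in deriving BOR". Protocol 7.4.1.2.2 is to the same effect. Once their response is confirmed, these patients enter the DoR analysis.

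**The concern.** The three endpoints use the same scans but not the same progression event. A patient can be progression-free for PFS, a responder for ORR, and already progressed for DoR. Two kinds of patient are affected:

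- A responder whose PD during response is not confirmed has DoR stopped at that PD, while PFS runs on.
- A patient whose response follows an unconfirmed PD has a first documented PD dated before the response began. The text then gives no usable end date.

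DoR is a named secondary endpoint, and protocol 7.4 lists it among the key ones. The additional scan after suspected pseudoprogression is planned for Arm 1 (protocol 2.2.1 and 6.4, SAP 6.4), and protocol 8.1.1 does not let FOLFOX-alone patients continue treatment past initial PD. Whatever error results therefore sits essentially in one arm of a descriptive between-arm display.

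**Working it through.** The plan states no DoR figure to reproduce. The check applies the written rules to assumed patient timelines and then sizes the effect on a median.

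**Inputs from the documents.** Scans at week 8 and every 8 weeks (protocol 6.4); an extra scan 4 weeks after suspected pseudoprogression (SAP 6.4); one month = 30.4375 days (SAP 7.2).

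**Formula.** DoR = end date − date of first documented response.

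**Timeline 1: unconfirmed PD during response.** PR week 8, confirmed week 12; PD week 24, not confirmed week 28; PD week 40, which is the PFS event.

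- As written: 24 − 8 = 16 weeks = 112 days = 112/30.4375 = 3.68 months.
- On the PFS date: 40 − 8 = 32 weeks = 224 days = 7.36 months.
- PFS is 40 weeks (280 days), so the DoR event comes 16 weeks before the same patient's PFS event.

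**Timeline 2: response after an unconfirmed PD.** PD week 8; PR at the week 12 rescan, later confirmed; confirmed PD first seen week 32.

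- First documented PD taken literally: 8 − 12 = −4 weeks (−28 days).
- First PD after response onset, a condition the text does not state: 32 − 12 = 20 weeks (140 days), equal to the PFS-aligned value.

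**Control.** Arm 2, PR week 8, PD week 40: DoR is 32 weeks under either rule.

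**Effect on the Arm 1 median.** All of the following are assumptions: exponential DoR with true median 24 weeks (λ = ln 2/24); a share q of Arm 1 responders with one unconfirmed PD, half before and half during response; a PD during response falling uniformly over that response. If s is the share of analysed responders cut short, the observed median m solves

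(1 − s)·exp(−λm) + s·E(m) = 0.5, where E(m) = ∫₀¹ exp(−λm/u) du.

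If timeline 2 patients have no valid DoR and drop out, s = (q/2)/(1 − q/2). If they are kept under the unwritten after-response condition, s = q/2.

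| q | s, dropped | median (shift), dropped | s, kept | median (shift), kept |
|---|---|---|---|---|
| 5% | 0.0256 | 23.53 (−0.47) | 0.025 | 23.55 (−0.45) |
| 10% | 0.0526 | 23.04 (−0.96) | 0.050 | 23.09 (−0.91) |
| 20% | 0.1111 | 21.99 (−2.01) | 0.100 | 22.19 (−1.81) |

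Check of the 20% dropped row: 0.8889 × 0.530 + 0.1111 × 0.261 = 0.471 + 0.029 = 0.500. The shift is about 0.5 to 2 weeks either way.

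**The case against.** The best defence is that the authors meant one progression date throughout. The PFS headline also speaks of first documented progression, and only the later bullets qualify it; DoR could be read with the same qualification. SAP 11.2.2 limits ORR to responses before progression as defined in section 10.2.1. No such section exists, and the evident target is 11.2.1. The SAP also treats pseudoprogression as distinct from progression: only PFS sensitivity analysis 3 (SAP 11.3.5) counts it as an event. This makes the PFS-aligned reading the likely intention, but it does not put it in the text. The sentence in 11.3.2 imports censoring, whereas the pseudoprogression bullets stand outside the censoring list and set the event date.

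A reader might infer that the plan produces negative durations. The documents do not support that as a certain result. DoR runs from a response to its end, and most programmers would take the first progression after onset, which removes the negative value in timeline 2. Two things remain: that condition is unwritten, and it leaves timeline 1 at half its PFS-aligned length.

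The defence is also right that few patients are probably involved. In the Phase 1b FOLFOX cohort (protocol 1.3.2), 3 of 21 patients had an irCR or irPR. Assuming the same rate in 283 Arm 1 patients gives 283 × 3/21 ≈ 40 responders, and 5–20% of those is about 2 to 8. That cohort used immune-related criteria, so this is only a rough guide.

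**Conclusion.** The inconsistency is real and appears in both documents. As written, an unconfirmed PD during response cuts DoR short, by 16 of 32 weeks in the example. A response that follows an unconfirmed PD has an undefined or negative DoR unless an unwritten condition is added. The distortion falls on Arm 1 and only on the affected responders; other Arm 1 durations are unchanged.

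Its size in the trial is unknown, because neither document gives a pseudoprogression rate. Under the assumptions shown, the Arm 1 median falls by about 0.5 to 2 weeks, which is small against an 8-week scan interval.

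A reader might infer a threat to the trial's efficacy conclusions. The documents do not support that. SAP 11.3.2 summarises DoR descriptively, the testing sequence in SAP 11.4 is OS, PFS, ORR, and the shortening works against AM0010. This is worth correcting because a named secondary endpoint would otherwise disagree with PFS and best response on the same scans.

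**What to change.** In SAP 11.3.2, with matching wording in SAP 6.2.2 and protocol 2.3.2, 7.4.1.2.4 and 7.5.4.5, state that response ends at the same progression event and date used for PFS in SAP 11.2.1, including its pseudoprogression rules, counting only progression after the first documented response, or at death. Correct the cross-reference in SAP 11.2.2 from 10.2.1 to 11.2.1.

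The passages on treatment past initial PD also need reconciling: protocol 2.2.1 and SAP 6.4 describe it for combination treatment, and protocol 8.1.1 for maintenance cycles. Tying DoR to the PFS event works whichever text is kept.

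A first-PD version of DoR beside PFS sensitivity analysis 3, limited to responses that begin before the first PD, is optional.

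Cost: a sentence of wording in each place. No new data are needed, and the program reuses the PFS event flag and date.
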